8.2 Operational definitions for (S)AEs

An AE is any untoward medical occurrence in a subject administered a pharmaceutical product and which does not necessarily have a causal relationship with the study treatments. An AE can therefore be any unfavourable and/or unintended sign (including an abnormal laboratory finding), symptom, or disease temporally associated with the use of an IMP, whether or not considered related to the IMP.

AEs observed by the Investigator, or reported by the subject, and any remedial action taken, will be recorded in the subject's CRF and should be verifiable in the subject's notes throughout the study. The nature of each event, time of onset after drug administration, duration and severity will be documented together with the Investigator's opinion of the causal relationship to the investigational product (unrelated, unlikely, possible, probable, and definite).

All subjects experiencing AEs, whether considered associated with the use of the study medication or not, must be monitored until the symptoms subside and any clinically relevant changes in laboratory values have returned to baseline, or until there is a satisfactory explanation for the changes observed.

Procedures such as surgery should not be reported as AEs. However, the medical condition for which the procedure was performed should be reported if it meets the definition of an AE. For example, an acute appendicitis that begins during the AE reporting period should be reported as the AE and the resulting appendectomy noted on the CRF.

Planned procedures such as surgery scheduled prior to the subject's enrolment into the study do not need to be reported as AEs if these are documented as planned at the screening visit.

Clinically significant changes in physical examination and blood safety profiles should also be recorded as AEs.

8.2.1 Assessment of intensity

Severity should be recorded and graded according to the ACTG Grading Scale (Appendix 2).

Note: There is a distinction between the seriousness and the intensity of an AE. Severe is a measure of intensity; thus, a severe reaction is not necessarily an SAE. For example, a headache may be severe in intensity but would not be classified as serious unless it meets one of the seriousness criteria for serious events.

All events deemed to be Grade 4 (potentially life threatening) according to the ACTG grading scale should be routinely reported as an SAE. However, there may be occasions where in the investigator's clinical judgement they do not consider the event to be life threatening therefore they do not consider the event to meet the definition of an SAE. In these cases, the investigator must document clearly in the participants source documentation that the Grade 4 event has been assessed and why in their clinical judgement they do not consider the event to be life threatening.

8.2.2 Assessment of causality

The relationship to study drug of each AE will be assessed by the PI (or a delegated clinician) using the following definitions:

DEFINITE: distinct temporal relationship with drug treatment. Known reaction to agent or chemical group or predicted by known pharmacology. Event cannot be explained by subject's clinical state or other factors.

PROBABLE: reasonable temporal relationship with drug treatment. Likely to be known reaction to agent or chemical group or predicted by known pharmacology. Event cannot easily be explained by subject's clinical state or other factors.

POSSIBLE: reasonable temporal relationship with drug treatment. Event could be explained by subject's clinical state or other factors.

UNLIKELY: poor temporal relationship with drug treatment. Event easily explained by subject's clinical state or other factors.

UNRELATED: the event occurs prior to dosing. Event or intercurrent illness is due wholly to factors other than drug treatment.

8.2.3 Collection and Follow up of Adverse Events

All AEs, however minor, will be documented in the CRF whether or not the Investigator considers the event to be treatment related.

The AE reporting period will be from consent until the subject's final study visit. In addition, any untoward event that may occur subsequent to the reporting period that the Investigator assesses as possibly, probably or definitely related to the study drug medication should also be reported as an AE.

AEs not already reported in the RSI for the study drugs will be considered unexpected.

AEs may be directly observed, reported spontaneously by the subject or by questioning the subject at each study visit.

All AEs should be followed up until they are resolved or the subject's participation in the study ends (i.e. until the final CRF is completed for that subject). In addition, all serious and non-serious AEs assessed by the Investigator as possibly related to the investigational medication should continue to be followed up to last subject visit. Such events should be followed until resolution, until no further change can reasonably be expected, or until 30 days following last subject visit.

8.3 Serious Adverse Events (SAEs)

Definition of an SAE can be found in section 8.1.

The SAE should be reported to the sponsor using the study specific SAE form within 24 hours of a member of the study team becoming aware of the event via the fax number provided on the study pharmacovigilance plan.

8.3.1 Recording and Reporting of SAEs and SUSARs

All SAEs/SUSARs occurring from the time of written informed consent until 30 days post cessation of trial treatment must be recorded on the study specific SAE Form and sent to the sponsor within 24 hours of the research staff becoming aware of the event.

For each SAE/SUSAR the following information will be collected:

- full details in medical terms and case description
- event duration (start and end dates, if applicable)
- action taken
- outcome
- seriousness criteria
- causality (i.e. relatedness to trial drug / investigation), in the opinion of the Investigator
- whether the event would be considered expected or unexpected

Any change of condition or other follow-up information should be sent to the sponsor as soon as it is available or at least within 24 hours of the information becoming available. Events will be followed up until the event has resolved or a final outcome has been reached.

All SAEs assigned by the PI or delegate (or following central review) as both suspected to be related to IMP-treatment and assessed by the CI as unexpected will be classified as SUSARs. The sponsor will inform the CA, the IRB/IEC and the funder as appropriate of SUSARs within the required expedited reporting timescales.

8.4 Responsibilities

8.4.1 Principal Investigator (PI):

Checking for AEs and ARs when participants attend for treatment / follow-up.

1. Using medical judgement in assigning seriousness and causality using the RSI approved for the trial.
2. Ensuring that all SAEs and SARs (including SUSARs) are recorded and reported to the Sponsor within 24 hours of becoming aware of the event and provide further follow-up information as soon as available.

3. Ensuring that SAEs and SARs (including SUSARs) are followed up with the Sponsor if a record of receipt is not received within 2 working days of initial reporting.
4. Ensuring that AEs and ARs are recorded and reported to the Sponsor in line with the requirements of the protocol.

8.4.2 Chief Investigator (CI) / delegate or independent clinical reviewer:

1. Clinical oversight of the safety of patients participating in the trial, including an ongoing review of the risk / benefit.
2. Using medical judgement in reviewing seriousness and causality of SAEs reported.
3. Using medical judgement in assignment of expectedness for all SARs reported using the approved RSI for the trial.
4. Review of specific SAEs and SARs in accordance with the trial risk assessment, protocol and as detailed in the Trial Risk Based Monitoring Plan.
5. Ensure immediate review of all SUSARs.
6. Assigning Medical Dictionary for Regulatory Activities (MedDRA) or Body System coding to all SAEs and SARs as needed.
7. Preparing the clinical sections and final sign off of the Development Safety Update Report (DSUR).

8.4.3 Sponsor:

1. Central data collection and verification of AEs, ARs, SAEs, SARs and SUSARs according to the trial protocol.
2. Reporting safety information to the CI, delegate or independent clinical reviewer for the ongoing assessment of the risk / benefit according to the Trial Risk Based Monitoring Plan.
3. Reporting safety information to the independent oversight committees identified for the trial (Data Safety Monitoring Board (DSMB)/Trial Steering Committee (TSC)) according to the Trial Risk Based Monitoring Plan and committee charter documents.
4. Expedited reporting of SUSARs to the CA and IRB/IEC within required timelines.
5. Notifying Investigators of SUSARs that occur within the trial.
6. Checking for (at least annually) and notifying PIs of updates to the RSI for the trial.
7. Preparing standard tables and other relevant information for the DSUR in collaboration with the CI and ensuring timely submission to the CA and IRB/IEC.

8.4.4 Data Safety Monitoring Board (DSMB):

In accordance with the DSMB Charter, periodically reviewing overall blinded safety data to determine patterns and trends of events, or to identify safety issues, which would not be apparent on an individual case basis.

8.4.5 Trial Steering Committee (TSC):

In accordance with the Trial Terms of Reference for the TSC, periodically reviewing unblinded safety data and liaising with the DSMB regarding safety issues.

8.5 Notification of deaths

Any AE, AR or unexpected AR that results in death should be reported as an SAE. See section 8.3 for SAE reporting format and timelines.

Deaths occurring more than 30 days after the final dose, which are considered to be unrelated to the study medication, should not be reported as an SAE.

8.6 Pregnancy reporting

Pregnancy information for all female participants who become pregnant while participating in the study will be collected on the study specific Pregnancy Reporting Form and should be reported to the Sponsor within 24 hours of becoming aware of the pregnancy or the pregnancy outcome. The participant will also be followed up to determine the outcome of the pregnancy, which will also be reported to the sponsor.

In the event of pregnancy, the participant may be withdrawn from the study (see Section 6.5).

Pregnancies in female partners of male participants should be reported as a special reporting situation (see Section 8.10).

8.7 Overdose

All participants should be counselled about the importance of taking the medications as prescribed and they should understand the quantity of medicine they should be taking. Participants must be told to contact their clinic immediately if they take too much medication. If the overdose fits the criteria of an SAE (see Section 8.1) it should be reported appropriately.

8.8 Reporting urgent safety measures

It is the responsibility of the investigator to apply the appropriate level of Urgent Safety Measure (USM) for the safety and protection of each participant in this study in order to prevent harm. USMs may be applied immediately without prior approval from the sponsor, CA or IRB/IEC. However, they must be reported to the sponsor immediately (within 24 hours) who will then inform the CA and IRB/IEC according to local regulation.

8.9 Development Safety Update Reports

The sponsor will provide (in addition to the expedited reporting above) DSURs once a year throughout the clinical trial, or on request, to the CA and IRB/IEC.

The report will be submitted within 60 days of the Developmental International Birth Date (DIBD) of the trial each year until the trial is declared ended.

8.10 Special Reporting Situations

Special reporting situations should be reported via email to the sponsor within 24 hours of the research staff becoming aware of the event (as for SAEs).

The special situations include:

- Pregnancy exposure (maternal and paternal), breastfeeding and AEs in infants following exposure from breastfeeding
- Overdose (other than as defined in section 8.7), suspected abuse/misuse of the study product, and dependence
- Medication error
- DDI
- Inadvertent or accidental exposure to the study product (including occupational exposure)
- Any failure of expected pharmacological or medical device action (i.e. lack of effect) of study product
- Unexpected therapeutic or clinical benefit from use of the study product

- Suspected transmission of an infectious agent via the study product
- Expired drug use and falsified medicine
- Off-label use of study product

Product Quality Complaint (PQC): Any written, electronic, or oral communication that alleges deficiencies related to the identity, quality, durability, reliability, safety, effectiveness, or performance of a study product after it is released for distribution. A complaint is any indication of the failure of the product to meet consumer or user expectations for quality or to meet performance specifications. It may allege an AR, injury, or malfunction associated with the use of the product. It may also involve the design, literature, packaging, advertising, availability, physical appearance, or promotion of a product.

9 STATISTICS AND DATA ANALYSIS

9.1 Sample size calculation

In the ANRS 146 OPTIMAL trial [Levy et al.], of late presenters, the proportion of patients with severe morbidity (new adverse drug event (ADE), other HIV related diseases, serious non-AIDS events, IRIS and death) was estimated at 12.2% per year in the boosted PI arm. The virological failure was estimated at 20% at week 48 in the DRV/r group of the IMEA 040 DATA study (Slama L et al) that recruited a similar population. As a few subjects will meet more than one of these criteria, we assumed a cumulative probability of failure at 25% at 48 weeks in the PI regimen group.

A total of 404 evaluable subjects, randomized in a 1:1 ratio to 2 treatment groups (202 subjects per treatment group), achieves at least 80% power to detect a non-inferiority margin of 1.606 in the hazard ratio, which corresponds to a 12% difference in the cumulative probability of failure rate between INI-based regimen group (37%) and PI-based regimen group (25%), with 97 events required. The sample size and power calculation assumes that the cumulative probability of failure is 25% for the PI regimen group and 23% for the INI-based regimen group (i.e. the expected hazard ratio is 0.909), using a non-inferiority margin of 1.606 in hazard ratio and a two-sided 95% confidence interval (CI). The sample size and power calculation were made using the statistical software package nQuery Advanced, non-inferiority testing of two survival curves using cox regression module (Version 8.1.2.0). With an estimated ~7.5% drop off rate/year, we plan to enroll 220 subjects per group to ensure we have sufficient power for this per-protocol analysis.

Superiority of INI-based regimen group versus PI-based regimen group will be evaluated after the non-inferiority is established. With an ITT analysis, 440 subjects and 78 events, a two-sided log-rank test at an alpha level of 0.05 will achieve at least 80% power to detect a 50% reduction in hazard rate in INI-based regimen (i.e. the hazard ratio is 0.5). A 50% reduction in hazard rate means that INI-based regimen could decrease the risk by 11.6% (25% for PI- vs 13.4% for INI- based regimen).

9.2 Planned recruitment rate

In the ANRS 146 OPTIMAL trial, in which similar patients were enrolled (late presenters with low CD4 cell count or ADE), 10% of screened patients were not eligible. Based on this information, we estimated that about 489 patients should be screened. Centres of NEAT ID Network with infectious disease units for inpatient and outpatient care will be the prioritised study sites of the LAPTOP Trial. We expect that about 45 sites in total across eight European countries. Therefore, we estimated that about 7-15 patients should be screened per site.

9.3 Statistical analysis plan

These analyses will assess the efficacy and safety of BIC containing regimen in comparison with the boosted PI containing regimen.

All randomised patients who received at least 1 time any study treatment will be included in the intent-to-treat (ITT) analysis population. Of note patients lost-to follow-up or violating the protocol will not be excluded from the ITT population. Patients who switch treatment to another will be analysed as if they are remained in their initial randomisation group. All participants who are lost to follow-up or discontinued the study when they are endpoint free at time of leaving the study will be censored at the time of leaving the study. We will use time-to-event methods, including Kaplan–Meier survival curves and Cox proportional-hazards models to account for all participants in the analysis. The per-protocol population will include all patients from the ITT population except those who did not fulfil the inclusion/exclusion criteria, who withdrew their consent, gave up, lost to follow-up or discontinued early study medication for any reasons other than any component of the primary endpoint.

9.3.1 Summary of baseline data and flow of patients

All continuous variables will be summarised using the following descriptive statistics: n (non-missing sample size), mean, standard deviation (SD), 1st quartile, median, 3rd quartile, maximum and minimum. The frequency and percentages (based on the non-missing sample size) of observed levels will be reported for all categorical variables.

The number of patients and the flowchart of the study will be presented. The period of enrolment and the total number of patients screened to be included in the study will be presented. The number of ineligible patients and the total number of randomised patients will be presented. The number of patients who never take the study treatment will also be presented by group and those who remained on the study treatment up to week 48 will be presented.

9.3.2 Primary outcome analysis

The primary outcome analysis will be performed with both ITT population and per-protocol population. The primary endpoint is the occurrence of a severe morbidity (virological failure; death related to HIV, AIDS, OI/severe BI or complications of therapy including IRIS; new ADE; new serious non-AIDS events; and clinically relevant AEs of any grade leading to study treatment discontinuation). The effect of study treatment will be assessed using Cox regression model with treatment group and adjustments for stratification factor (participating country and baseline CD4 cell counts). Separate analyses for each component of the primary endpoint will be done. Kaplan-Meier curves will be plotted for the primary endpoint and its component.

9.3.3 Secondary outcome analysis

All secondary outcome analysis will be done with the ITT population. The p-values will be two-tailed, with a significant level of 0.05.

The proportion of patients with HIV-ribonucleic acid (RNA) viral load <50 copies/mL at week 48 will be analysed using the snapshot approach. Fisher's exact test will be used to compare the estimated proportion between the two groups.

A genotypic resistance test will be performed in all patients with virological failure. Drugs resistance mutations will be identified from the International AIDS Society (IAS)-USA resistance testing panel (last version at the time of analysis) and for BIC we will use IAS, Agence Nationale de Recherches sur le SIDA (National Agency for AIDS Research) (ANRS) or Royal College of Physicians (RCP) lists to perform the analysis whenever they will be made available. Resistance to BIC will also be identified using

phenotypic resistance test. Fisher's exact test will be used to compare the presence of at least one drug resistance mutation between the 2 groups.

The median time to reach CD4 cell count $>200/\mu\text{l}$ will be estimated using the Kaplan-Meier method, censoring at week 48 or last follow-up date if not seen at week 48. Time to reach CD4 cell count $>200/\mu\text{l}$ will be defined as the time between the date of study treatment initiation (baseline, week 0) and the date of which patient reached CD4 $>200/\mu\text{l}$. The log-rank test will be used to compare the two survival functions. The p-values will be two-tailed, with a significant level of 0.05. The proportion of patients with CD4 cell count $<350/\mu\text{l}$ at week 48 will be done with the ITT population, with the last observation carried forward (LOCF) approach. Fisher's exact test will be used to compare the 2 groups.

The median change in CD4/CD8 ratio from baseline to week 48 will be analysed with the ITT population, with the LOCF approach. The non-parametric Mann Whitney test will be used to compare the change from baseline between the 2 groups.

The incidence of IRIS will be analysed with the Kaplan-Meier method. The Log-rank test will be used to compare the two survival functions. The effect of study treatment on IRIS will be assessed using Cox regression model with treatment group and adjustments for stratification factors.

The incidence of hospitalisation will be estimated by the Kaplan-Meier estimate. The Log-rank test will be used to compare the two survival functions. The duration of hospitalisation will be estimated by the cumulative days of hospitalisation during the course of study and will be compared between the 2 groups by using the Mann-Whitney test. The rate of relapse/recurrence will be estimated by the number of patients with relapse/recurrence divided by the total number patients in ITT population. Fisher's exact test will be used to compare the 2 groups.

The frequency of each Grade 2, 3 or 4 AEs, laboratory toxicities, and ART and OI/BI treatment changes and dose modifications due to toxicities and IRIS will be described and compared by group. Fisher's exact test will be used to compare the 2 groups.

The proportion of patients with health care resource use, and emergency room visits will be compared in the two groups with Fisher's exact test. The total inpatient days will be estimated by the cumulative inpatient days during the course of study and will be compared between the 2 groups by using the Mann-Whitney test.

To assess the impact of study treatment on the evolution of QOL at week 48, we will use multiple imputation approach to replace missing values. We will compare the treatment effect on QOL on each of the 5 datasets generated, including the imputed values, and the results will be combined with Rubin's rules. A generalized estimating equation (GEE) model will be used.

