7.2.10 Rate of relapse/recurrence of specific opportunistic infection or bacterial infection

through week 48

Endpoint

The endpoint is the rate of relapse/recurrence of specific opportunistic infection or bacterial infection through week 48.

Descriptive statistics and graphical representation

The analyses will be performed with the mITT population and DPS1. Data will be summarized with the number and percentage of participants with relapse/recurrence of specific opportunistic infection or bacterial infection through week 48.

Statistical methodology

The rate of relapse/recurrence will be estimated by the number of patients with relapse/recurrence divided by the total number patients in ITT population.

The effect of study treatment on the rate of relapse/recurrence of specific opportunistic infection or bacterial infection at week 48 will be assessed using a logistic regression model with treatment group and adjustments for stratification factor (country/group of neighbouring countries and baseline CD4 cell counts (<50 or \geq 50/ μ L)). An adjusted odds ratio (OR) and the associated 95% Confidence Interval (CI) will be calculated.

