10. OTHER ANALYSES

10.1 OTHER SECONDARY ENDPOINTS

10.1.1 ART and/or opportunistic infection/bacterial infection treatment changes and/or dose modifications due to toxicities and/or DDI with ART, and/or IRIS through week 48

Endpoint

The endpoint is the proportion of patients with ART treatment changes and/or dose modifications due to toxicities and/or DDI with ART, and/or IRIS through week 48.

Descriptive statistics and graphical representation

The analyses will be performed with the mITT population and DPS1. Data will be summarised with the number and percentage of participants with ART or OI/BI treatment changes or dose modifications due to toxicities and DDI and IRIS through week 48. The list of patients with the event of interest will be reported in a table, including the previous and the current treatment, start date, end date and the reason for change.

Statistical methodology

The percentage of patients with ART n treatment changes due to toxicities and/or DDI with ART, and/or IRIS will be estimated by the number of patients with the event of interest divided by the total number patients in ITT population. The effect of study treatment on the proportion of patients with ART treatment changes due to toxicities and/or DDI with ART, and/or IRIS at week 48 will be assessed using a logistic regression model with treatment group and adjustments for stratification factor (country/group of neighbouring countries and baseline CD4 cell counts (<50 or \geq 50/ μ L)). An adjusted odds ratio (OR) and the associated 95% Confidence Interval (CI) will be calculated. Similar analyses will also be performed separately for each component (toxicities, DDI, and IRIS). If no events were observed in a group, the comparison will be made using Fisher's exact test.

10.1.2 Health care resource use, through week 48

Endpoint

The endpoint is the proportion of patients with health care resource use, through week 48.

Descriptive statistics and graphical representation

The analyses will be performed with the mITT population and DPS1. Data will be summarised with the number and percentage of participants with health care resource use, including total inpatient days and emergency room visits through week 48.

Statistical methodology

The percentage of patients with health care resource use, including total inpatient days and emergency room visits will be estimated by the number of patients with the event of interest divided by the total number patients in ITT population.

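### Four secondary event proportions to week 48 count participants who leave early as event-free: a small weakness that follow-up time would remove

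*Combined protocol and SAP*

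**What the plan says.** Protocol 9.3.3 reads the same in v1.5 and v5.0. It begins: "All secondary outcome analysis will be done with the ITT population". Section 9.3 defines that population: "All randomised patients who received at least 1 time any study treatment will be included in the intent-to-treat (ITT) analysis population". For relapse, the count of affected patients is "divided by the total number patients in ITT population. Fisher's exact test will be used to compare the 2 groups". For health care use: "The proportion of patients with health care resource use, and emergency room visits will be compared in the two groups", again with Fisher's exact test. Treatment changes are also compared by Fisher's exact test. Section 9.3.3 names no method for drug changes due to response or resistance.

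The SAP replaces Fisher's test with logistic regression adjusted for country group and baseline CD4, but keeps the denominator. In 10.1.1, 10.1.2 and 10.1.4 the percentage "will be estimated by the number of patients with the event of interest divided by the total number patients in ITT population". Section 7.2.10 uses the same ratio and gives the logistic model for this quantity: "The effect of study treatment on the rate of relapse/recurrence of specific opportunistic infection or bacterial infection at week 48". The SAP's mITT set is the set the protocol calls ITT.

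Other outcomes in the same documents do use follow-up time. In the protocol, "The incidence of IRIS will be analysed with the Kaplan-Meier method". SAP 7.2.7 (IRIS) and 7.2.8 (hospitalisation) use Kaplan-Meier and an adjusted Cox model. SAP section 8 uses person-years and Poisson regression for adverse events and laboratory toxicities, where the protocol had Fisher's test.

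**The concern.** Each of the four outcomes can be recorded only while the participant is under observation. Someone who leaves the study in week 3 without an event stays in the denominator for all 48 weeks and cannot enter the numerator.

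Nothing else in the SAP repairs this:
- Section 5.3 censors lost participants at their last observation, but a logistic or Fisher analysis has no way to use a censoring time. Its other rules do not cover unobserved yes/no events.
- DPS1 keeps everything that was observed and adds nothing for unobserved time.
- The SAP's per-protocol set removes only ineligible or wrongly treated participants, so early leavers remain.

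At stake are slightly low proportions in both arms and, if one arm loses more people for reasons other than death, an odds ratio that drifts in that arm's favour. The trial is open-label, so unequal loss cannot be excluded in advance. The plan is also uneven: hospitalisation is censored in 7.2.8, while health care use, which includes inpatient days, is not censored in 10.1.2.

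**Working it through.** **Inputs.** About 7.5% loss per year and 220 per arm come from protocol 9.1 and SAP section 4; 7.5% is taken here as the loss over 48 weeks. The documents give no event risk for these four outcomes and no loss by arm. The 15% and 30% risks (10% to 40% in step 5) and the split losses are assumptions.

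**1. The plan's own figures.** None is stated for these endpoints, so the check is on the sample size that carries the 7.5%.
- Events: 4 × (1.960 + 0.842)² / (ln 1.606 − ln 0.909)² = 96.9, rounded up to 97, as stated.
- Evaluable: 97 / 0.24 = 404, as stated (0.24 is the mean of 25% and 23%).
- With loss: 202 / 0.925 = 218.4, so 219 per arm against 220 planned. The figures reproduce.

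**2. Formula.** Take a constant event hazard l = −ln(1 − p) and an independent constant loss hazard k = −ln(1 − d) over 48 weeks. The proportion the SAP would report is l/(l + k) × [1 − (1 − p)(1 − d)].

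**3. Same 7.5% loss in both arms.**
- p = 15%: l = 0.1625, k = 0.0780; 0.6758 × (1 − 0.85 × 0.925) = 0.6758 × 0.21375 = 0.144.
- p = 30%: l = 0.3567; 0.8206 × (1 − 0.70 × 0.925) = 0.8206 × 0.3525 = 0.289.
- Both arms fall equally, so with no true difference the odds ratio stays at 1.00.

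**4. Unequal loss, no true difference, p = 15%.** Losses of 11% and 4% average the planned 7.5%.
- Spread evenly: 0.5824 × 0.2435 = 0.1418, against 0.7992 × 0.1840 = 0.1471. Odds ratio = (0.1418/0.8582) / (0.1471/0.8529) = 0.96.
- All loss at the start: 0.15 × 0.89 = 0.1335, against 0.15 × 0.96 = 0.144. Odds ratio = (0.1335/0.8665) / (0.144/0.856) = 0.92.

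**5. Outer bound with the same average.** Put all the loss in one arm (0% v 15%, spread evenly). For true risks of 10% to 40% the spurious difference is 0.76 to 2.83 points. In 4,000 simulated trials with 220 per arm, type I error was as follows.

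| True risk | Odds ratio | Fisher | Chi-square (stand-in for logistic) | Log-rank |
|---|---|---|---|---|
| 20% | 0.91 | 5.9% | 7.2% | 5.2% |
| 40% | 0.89 | 7.6% | 9.1% | 5.0% |

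**6. Scale.** At 15% risk each arm has 0.15 × 220 = 33 events. The standard error of the log odds ratio is √[2 × (1/33 + 1/187)] = 0.27, so a 95% interval around 1 runs from about 0.59 to 1.69. An odds ratio of 0.96 is about 0.16 standard errors from 1.

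**The case against.** The strongest case for leaving the text alone has five parts.

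- **Death.** A reader might infer that scoring a participant who dies first as event-free is itself an error. It is not. A cumulative incidence with death as a competing event does the same, and the SAP compares deaths by arm separately. This stands: only loss other than death is at issue.
- **No evidence of imbalance.** A reader might also infer that the arm losing more patients will in practice look better. The documents give one pooled loss rate and nothing that points to a difference between arms. This stands: the between-arm bias is conditional.
- **Tolerability is covered elsewhere.** Adverse events, including those leading to discontinuation, use person-years. Treatment interruption for adverse events or IRIS is a component of the primary endpoint and is analysed by Cox regression. Recurrent AIDS events, severe bacterial infection and virological failure are also primary components and overlap two of the four outcomes. This stands, so a claim that the trial's tolerability conclusions are compromised is not supported.
- **Loss is limited and visible.** Participants who stop study drug are encouraged to attend to week 48 (protocol 6.4), and SAP 6.1 tabulates who left, why and when. This reduces the problem and would reveal it, but it does not correct the four estimates.
- **A blanket switch to Cox has costs.** A hazard ratio is not finite when one arm has no events, which is why SAP 10.1.1 and 10.1.4 carry a Fisher fallback. The Appendix 1 flowchart has no health-care-use item, so dates of emergency visits are not shown to exist. Time to first event cannot express inpatient days. This stands and shapes the remedy.

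The censoring rule in SAP 5.3 is no answer, because it cannot act in the models specified.

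**Conclusion.** The weakness is real, confined to four secondary endpoints, and small. At the planned loss the proportions read low by roughly 0.6 points at 15% risk (15.0 − 14.4) and 1.1 points at 30% (30.0 − 28.9). Between-arm bias appears only when loss other than death is unequal. With losses averaging the planned rate, it moves the odds ratio to 0.96 or 0.92 in the 11% v 4% cases, well inside the sampling error. Only a one-sided split of all the loss raises false-positive rates noticeably.

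These sizes rest on assumed event risks, assumed loss by arm, constant hazards where loss is spread evenly, and loss unrelated to the event. The analyses of the primary endpoint, IRIS, hospitalisation, adverse events and laboratory toxicities are not touched. The change is worth making because a better method is already written into the same SAP, not because a conclusion is at risk.

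**What to change.** - **SAP 7.2.10, 10.1.1 and 10.1.4.** Analyse time to first event from first dose to the week-48 visit or last observation. Use the adjusted Cox model of 7.2.7 and 7.2.8. Report week-48 cumulative incidence by arm with death as a competing event and other early leavers censored.
- **Arms without events.** Keep a named fallback: the log-rank test, or the existing Fisher test.
- **SAP 10.1.2.** Do the same for emergency visits if their dates are recorded. Otherwise use a person-year rate with Poisson regression, as in section 8. Keep inpatient days as a separate burden measure, which protocol 9.3.3 already compares by the Mann-Whitney test.
- **Alignment.** Amend protocol 9.3.3 and the columns of SAP Table 8 to match.

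The cost is mainly wording and table shells. SAP 10.1.1 already lists start and end dates of treatment changes, protocol 6.5 requires the date of stopping medication on the case report form, and SAP 5.3 has a rule for missing onset dates of clinical endpoint events. Dates of emergency visits must be confirmed before that part is fixed. The effect measure changes from an odds ratio to a hazard ratio or rate ratio. Censoring assumes that leaving is unrelated to the event, so the reasons for leaving should be shown by arm beside the results.
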